8.1.10 Drug toxicities

The following drug toxicities were noted in trials mostly involving patients with myelofibrosis and polycythemia vera.

Blood and lymphatic system disorders:

Anemia (40.8-82.4%), thrombocytopenia (16.8-69.8%), neutropenia (16.6%). Also includes febrile neutropenia. Cytopenias are dose dependent and reversible with dose reduction/interruption.

Infections and infestations:

Urinary tract infections (6-12.6%) Including urosepsis, Cystitis, Kidney infection, Urinary tract infection bacterial, Nitrite urine present, and pyuria. Pneumonia (8.3%) Herpes zoster (4.0-4.3%) Tuberculosis (0.3%)

Gastrointestinal disorders:

Flatulence (3.3%) and Constipation (8.7%).

Hepatic dysfunction:

Raised alanine aminotransferase (22.3-27.2%) and aspartate aminotransferase (19.9-26.1%)

Metabolism and nutrition disorders:

Weight gain (7.6-12.3%), Hypercholesterolemia (16.9-20.7%), Hypertriglyceridemia (9.8%)

Nervous system disorders:

Dizziness (12.0-15.3%), Headache (14.0%)

Skin and subcutaneous tissue disorders:

Bruising (21.6%) including hematoma, petechiae and purpura

Vascular disorders:

Hypertension (6.5%)

General disorders and administration site conditions:

In clinical studies in myelofibrosis, fatigue, bone pain, pyrexia, pruritus, night sweats, splenomegaly and weight loss noted in 60.4% after discontinuation of ruxolitinib.

In a retrospective study of ruxolitinib in patients with chronic GVHD, cytopenia and CMV reactivation was observed in 17% and 15% of patients. Cytopenias preceded the use of ruxolitinib in most of the patients (15%).

Progressive Multifocal leukoencephalopathy (PML) has been reported with ruxolitinib treatment. Physicians should be alert for neuropsychiatric symptoms suggestive of PML. If PML is suspected, further dosing must be suspended until PML has been excluded.

Non-melanoma skin cancers (NMSCs), including basal cell, squamous cell, and Merkel cell carcinoma have been reported in patients treated with ruxolitinib. Most of these patients had histories of extended treatment with hydroxyurea and prior histories of NMSC or pre-malignant skin lesions. A causal relationship to ruxolitinib has not been established. Periodic skin examination is recommended for patients who are at increased risk for skin cancer.

8.1.11 Drug Accountability

Responsibility for drug accountability at the study site rests with the investigator; however, the investigator may assign some of the drug accountability duties to an appropriate pharmacist or designee. Inventory and accountability records must be maintained and readily available for inspection by the study monitor and are open to inspection at any time by any applicable regulatory authorities.

The investigator or designee will be expected to collect and retain all used, unused, and partially used containers of study medication until the end of the study. The Investigator or designee must maintain records that document:

- investigational product delivery to the study site
- the inventory at the site
- use by each subject including pill/unit counts from each supply dispensed
- product returned to the investigator or designee.

These records should include dates, quantities, batch/serial numbers (if available), and the unique code numbers (if available) assigned to the investigational product and study subjects.

The investigational product must be used only in accordance with the protocol. The investigator will also maintain records adequately documenting that the subjects were provided the study medication specified.

Completed accountability records will be archived by the site. If any unused ruxolitinib bottles remain at the end of the study, they will be accounted for by the site prior to study closure. If a site is able to destroy ruxolitinib at their premises, or through a certified vendor, they may do so upon authorization by the sponsor, provided their destruction policy is made available to the sponsor.

Section 9.0 Toxicity and Adverse Event Reporting Guidelines

This protocol will comply with monitoring and adverse event reporting requirements of the UNMC Fred & Pamela Buffett Cancer Center Data Monitoring plan. The protocol will adhere to the institutional and FDA guidelines for the toxicity reporting.

All subjects will be closely followed for toxicity from the time of informed consent until 30 days after last administration of study medication. The reporting is only for “study medication,” until 30 days after last administration of study medication.

Adverse events (AEs) will be assessed by reports from subjects to their physician/Investigator and by physical examinations. Per NCI guidelines, serious adverse events (SAEs) and AEs will be graded and toxicity will be assessed using the revised NCI CTCAE version 4.03 (Appendix H). Adverse event will be followed until resolution, baseline or \leq grade 1 levels.

Serious adverse events should be followed until resolution, baseline or \leq grade 1 levels, death, or until no further improvement is reasonably expected. Deaths occurring within 30 days of study treatment regardless of relationship will be reported to the Fred & Pamela Buffett Cancer Center Data and Safety Monitoring Committee (DSMC).

9.1 Definitions

Adverse Event

An adverse event (AE) is defined as any untoward medical occurrence in a clinical trial subject administered a pharmaceutical product and which does not necessarily have a causal relationship with this treatment. An adverse event can therefore be any unfavorable and unintended sign (including an abnormal laboratory finding, for example), symptom, or disease temporally associated with the use of a medicinal (investigational) product, whether or not the event is considered causally related to the use of the product.

An elective surgery or procedure that is scheduled to occur during a study will not be considered an adverse event if the surgery or procedure is being performed for a pre-existing condition and the surgery or procedure has been planned before study entry. However, if the pre-existing condition deteriorates unexpectedly during the study (*e.g.*, the surgery is performed earlier than planned), then the deterioration of the condition for which the elective surgery or procedure is being done will be considered an adverse event.

Any worsening of a pre-existing condition or illness is considered an adverse event. Laboratory abnormalities and changes in vital signs are considered to be adverse events if they result in discontinuation from the study, necessitate therapeutic medical intervention, require dose modifications and/or if the investigator considers them to be adverse events.

Unexpected Adverse Event

An unexpected adverse event is any adverse drug event that is not listed in the current labeling/Investigator's Brochure. "Unexpected," as used in this definition, refers to an adverse drug experience that has not been previously observed (*i.e.*, included in the labeling) rather than from the perspective of such experience not being anticipated from the pharmacological properties of the pharmaceutical product.

Serious Adverse Event

A serious adverse event is one that at any dose (including overdose) and regardless of causality:

- Results in death
- Is a serious threat to life, health, safety or welfare-fare of subject ¹
- Requires inpatient hospitalization or prolongation of existing hospitalization
- Requires intervention to prevent permanent impairment or damage
- Results in persistent or significant disability or incapacity²
- Is a congenital anomaly or birth defect
- Is another serious important medical event³
- Is any medical event in an investigational drug study that requires treatment to prevent one of the outcomes listed above
- Seriously jeopardizes the rights, safety, or welfare of subjects

¹"Life-threatening" means that the subject was at immediate risk of death at the time of the serious adverse event; it does not refer to a serious adverse event that hypothetically might have caused death if it were more severe.

²"Persistent or significant disability or incapacity" means that there is a substantial disruption of a person's ability to carry out normal life functions.

³Medical and scientific judgment should be exercised in deciding whether expedited reporting is appropriate in situations where none of the outcomes listed above occurred. Important medical events that

may not be immediately life-threatening or result in death or hospitalization but may jeopardize the patient or may require intervention to prevent one of the other outcomes listed in the definition above should also usually be considered serious. Examples of such events include allergic bronchospasm requiring intensive treatment in an emergency room or at home, blood dyscrasias or convulsions that do not result in inpatient hospitalization, or the development of drug dependency or drug abuse. A new diagnosis of cancer during the course of a treatment should be considered as medically important.

9.2 Adverse Event Reporting and Definitions Per University of Nebraska Medical Center, IRB and Fred & Pamela Buffett Cancer Center Data and Safety Monitoring Committee (DSMC) and Incyte Corporation

This protocol will adhere to all institutional guidelines for adverse event reporting. Adverse events will be evaluated using the NCI Common Terminology Criteria for Adverse Events (CTCAE) version 4.03 (Appendix H).

9.2.1 IRB Reporting

All internal serious adverse events (AE) must be reported to the local IRB promptly per institutional policy and in no case later than two (2) business days following PI notification that the event occurred *if* the principal investigator determines that conditions A, and B, are met:

- a. The AE is unexpected, *AND*
- b. The AE is related to, or possibly related to, the drug, biologic, device, or other research intervention

All *unexpected*, internal, fatal AEs must be reported promptly to the local IRB per institutional policy, but no later than *24 hours* following PI notification that the event occurred. If documentation is still pending, the IRB office must be notified by a telephone call or e-mail.

All *expected*, internal, fatal AEs (i.e., due to progressive disease or which reflect a risk currently found in the consent form) must be reported to the local IRB per institutional policy no later than ten (10) business days following PI notification that the event occurred.

9.2.2 Fred & Pamela Buffett Cancer Center Data and Safety Monitoring Committee (DSMC) Reporting

In its initial review, the DSMC will make a recommendation for the frequency of DSMC monitoring based on an assessment of risk associated with study-associated therapy, per the DSMC policy. Reporting of the following will be done in accordance with DSMC guidelines:

- All Serious adverse events (SAEs) and toxicity reporting will be reported to the DSMC.
- All adverse events grade 3 or higher (expected or unexpected, regardless of attribution) will be reported to the DSMC.

Attribution of AE: The likelihood of relationship of the AE to the study drugs will be determined by the investigator based on the following definitions:

Not related: The subject was not exposed to the study treatment or another cause is obvious.

Probably not related: The AE is most likely explained by another cause, and the time of occurrence of the AE is not reasonably related to the study treatment.

Possibly related: Study treatment administration and AE occurrence reasonably related in time, and the AE is explained equally well by causes other than study treatment, or treatment administration and AE occurrence are not reasonably related in time, but the AE is not obviously a result of other causes.

Probably related: Study treatment administration and AE occurrence are reasonably related in time, and the AE is more likely explained by study treatment than by other mechanisms.

Definitely related: The occurrence and timing of the AE are clearly attributable to the study treatment.

AEs will be collected from the time the subject signs the consent form and ending 30 days following the final dose of study drug. All AEs will be followed until resolution, a cause is identified, or until no further improvement is expected. AEs judged by the investigator as not related or probably not related to the treatment will NOT be followed beyond the 30 days after the final dose of study drug.

All SAEs and AE reporting will be completed using DSMC approved forms. Detailed policy and procedures for this section may be reviewed at:

<http://www.unmc.edu/cancercenter/clinical/prms.html>

9.2.3 Incyte Reporting

To ensure subject safety, every Serious Adverse Event (SAE), occurring after the subject has consented and until at least 30 days after the subject has stopped taking the Incyte study product (ruxolitinib) must be reported to Incyte ***within twenty four (24) hours*** of learning of the event.

If a subject experiences a SAE after signing informed consent, but prior to receiving ruxolitinib, the event will NOT be collected unless the investigator feels the event may have been caused by a protocol procedure. Previously planned (prior to signing the informed consent document) surgeries should not be reported as SAEs unless the underlying medical condition has worsened during the course of the study.

All SAEs are to be captured on Incyte's Adverse Event Report Form.

The study sites will submit the SAEs to Incyte via [contact]. If critical or outstanding information is missing from the Adverse Event Report Form or additional clarification is needed, the Incyte representative will submit a Data Clarification Form (DCF) to the Sponsor-Investigator. The Sponsor will be required to complete all queries listed on the DCF and return the completed DCF to Incyte.

The Sponsor-Investigator must report to Incyte all Serious Adverse Events regardless of the causality assessment.

Follow- up Reporting

When new information regarding an SAE becomes available, this information must be reported to Incyte on a new or updated Adverse Event Report Form **twenty four (24) hours** of becoming aware of the information.

Reconciliation

On a periodic basis (quarterly at minimum), the Sponsor-Investigator will provide a listing of all Safety Information recorded for the study to Incyte for reconciliation purposes. The Sponsor-Investigator will forward the listing via email to [contact]

Interventional Investigator Initiated Trials

The Sponsor-Investigator reports all Suspect Unexpected Serious Adverse Reactions (SUSARs) to the relevant Health Authority where the Investigational New Drug (IND) was approved for the Sponsor-Investigator and distributes Investigator Notifications (IN) as required by local regulations.

Incyte will submit to the relevant Health Authorities outside of Sponsor-Investigator's approved countries and distributes Investigator Notifications to other Investigators as applicable.

- The Sponsor-Investigator will author the Development Safety Update Report (DSUR) and share the completed DSUR with Incyte for comment prior to submission to the health authority.

Pregnancies

Pregnancy, in and of itself, is not regarded as an adverse event, unless there is suspicion that study medication may have interfered with the effectiveness of a contraceptive medication or method. The procedures to be followed based on a confirmed pregnancy by a positive serum test result are listed below:

- Investigator and subject must notify each other immediately
- Investigator must notify the Investigator –Sponsor and Incyte immediately
- Discontinue study medication immediately
- Perform the required End-of-treatment visit study evaluations
- Investigator must complete and submit the Pregnancy Initial and Follow-up report forms to the Sponsor

To ensure subject safety, each pregnancy in a subject during maternal or paternal exposures to study drug must be reported within 24 hours of learning of its occurrence.

Any SAE experienced during pregnancy must be reported on the SAE Report Form and needs to be reported to the Investigator-Sponsor and Incyte.

9.3 Monitoring

Various methods will be implemented by the sponsor (UNMC) to exchange information with participating sites:

- Site Initiation/Orientation

- Regular Teleconferences including group wide progress within the agenda
- Investigator meetings as feasible (remote or on an as needed basis, possibly in conjunction with larger meetings)
- Email distributions/reports as needed

9.3.1 Data Monitoring

For this study, data monitoring is the act of overseeing the progress of a clinical trial, and of ensuring that it is conducted, recorded, and reported in accordance with the protocol, standard operating procedures (SOPs), Good Clinical Practice (GCP), and applicable regulatory requirement(s). Monitoring is a Quality Control, continuous process during the entire trial.

All participating sites will perform routine data monitoring for this study by each site's institution according to the institution's internal guidelines and policies. A copy of the site's monitoring report will be submitted to UNMC.

9.4 Auditing

Auditing is a systematic and independent examination of trial-related activities and documents to determine:

- whether the evaluated trial-related activities were conducted
- the data were recorded, analyzed, and accurately reported, according to the protocol, to the sponsor's SOPs, GCP, and applicable regulatory requirement(s).

Auditing is a Quality Assurance, one point process during the trial.

The UNMC Fred & Pamela Buffett Cancer Center Scientific Review Committee (SRC) will review this protocol on at least an annual basis.

This study will undergo audit on at least a semi-annual basis by the UNMC Fred & Pamela Buffett Cancer Center Audit Committee.

Detailed policy and procedures for this section may be reviewed at:
<https://www.unmc.edu/cancercenter/clinical/prms.html>.

Section 10.0 Statistical Considerations

10.1 Study Design and Sample Size Description

The study is an open label, phase II, multicenter trial designed to evaluate ruxolitinib as a salvage treatment for subjects with sclerotic GVHD (sclerosis or fasciitis).

If a subject receives one dose of ruxolitinib then the subject will be included in the safety analysis set.

The full analysis set will include all subjects that are evaluable at 6 months as well as subjects who are considered a treatment failure (including deaths) prior to 6 months. Subjects who drop out of the study prior to 6 months for reasons unrelated to treatment will be excluded from the full analysis set.

The primary endpoint is complete and partial responses in skin and/or joint, as determined by 2014 NIH Criteria (1) at 6 months from initiation of ruxolitinib without addition of any other systemic chronic GVHD treatment, relapse of the underlying disease, or death. The historical benchmark for overall response for steroid refractory sclerotic chronic GVHD is 25% in a randomized phase II trial by Arai et al., comparing imatinib and rituximab (15). In the trial by Arai et al., a significant clinical response was defined as “2 or more point improvement on the Vienna Skin Score without worsening elsewhere or at least a 1-point improvement in the 4-level P-ROM scale or a 2-point improvement in the 7-level scale without worsening elsewhere.” The Vienna Skin Score is different from the 2014 NIH criteria (1) for responses in skin and/or joint. According to the 2014 NIH guidelines (1), “because the NIH 0 to 3 Skin Score is now recommended for response assessment, even substantial improvement in sclerotic features will not be considered responses unless the NIH Skin Score improves.” For this reason, for the purpose of the stopping rules, responses will include complete and partial responses in skin and/or joint, at least a 2-point improvement on 0-10 semiquantitative scale for capturing clinician-perceived severity of sclerosis, or clinically significant improvement (improvement by ≥ 6 point) on the skin subscale of the Lee symptom scale, consistent with the recommendations of the 2014 NIH Criteria (1). Additionally, improvement in percentage of BSA involved with deep sclerosis/fasciitis will also be taken into consideration as a marker of responses.

A two-stage design is planned to test the null hypothesis that the overall response rate $p \leq 0.250$ versus the alternative that $p \geq 0.450$. The first stage will occur once 18 subjects have completed 6 months of treatment. If only 4 or fewer out of the 18 subjects respond at the end of 6 months of treatment, the trial will be stopped for futility. At stage two, an additional 24 subjects will be enrolled for a combined total of 42 from both stages. If only 15 or fewer respond out of 42 subjects at the end of stage two, then no further investigation is warranted. If 16 or more respond then further investigation is warranted. This design achieves 84% power with a significance level of 0.044. Retrospective studies (31, 32, 40) have demonstrated that ruxolitinib is well tolerated and effective in patients with steroid-refractory chronic graft-versus-host disease (GVHD) in general and sclerotic GVHD. Therefore, the accrual will not be put on hold for interim analysis.

To meet our statistical endpoints, a sample size of 42 is required; however, to account for dropout rate of approximately 10%, the study will dose 47 subjects.

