Chronic graft-versus-host-disease (GVHD) is a major complication of allogeneic hematopoietic cell transplant that impairs quality of life, and is associated with significant morbidity and mortality. Management of chronic GVHD with prednisone is associated with an overall response rate of approximately 60%, and a complete response rate of approximately 30% but sclerotic features do not respond as well. Based on the biology of chronic GVHD and available preliminary evidence, we hypothesize that ruxolitinib will be effective in the management of sclerotic chronic GVHD. The study is an open label, phase II multicenter trial designed to evaluate the efficacy of ruxolitinib as a salvage treatment for subjects with sclerotic GVHD (sclerosis or fasciitis). The primary objective is to determine the proportion of subjects with response rate (complete and partial responses) in skin and/or joint, as determined by 2014 NIH consensus criteria, at 6 months of therapy with ruxolitinib. Eligibility criteria includes adult subjects with chronic GVHD and skin, joint and/or fascia sclerosis, who have received systemic corticosteroids for >12 months and at least one additional line of therapy OR systemic corticosteroids and at least two additional lines of therapy for chronic GVHD. A sample size of 47 subjects dosed (42 evaluable subjects and estimated 10% dropout) will allow an α of 0.044 and a power of 84% to test the null hypothesis response rate of 25% compared to an alternative of 45%. Subjects will receive ruxolitinib for 6 months for the treatment of sclerotic chronic GVHD. Subjects will be evaluated for GVHD status as well as non-relapse mortality, relapse of underlying malignancy and quality of life/functional status. Plasma cytokine levels and T/NK cell subset in peripheral blood will be measured at various time points. The response rate will be reported as a proportion and 95% exact confidence interval. If positive, the trial results will support other ongoing studies to establish the role of ruxolitinib in chronic GVHD in general and specifically in sclerotic chronic GVHD.

Study Schema

Patients with chronic graft-versus-host-disease and skin, joint and/or fascia sclerosis, who have received systemic corticosteroids for >12 months and at least one additional line of therapy OR systemic corticosteroids and at least two additional lines of therapy

Informed consent and registration

Ruxolitinib therapy for 6 months

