10.2.1 Efficacy Endpoints

Primary and secondary objectives

The primary objective of the study is to determine the complete and partial responses in skin and/or joint after 6 months of therapy. The response rate will be reported as a proportion and 95% exact confidence interval. This analysis will be conducted on the full analysis set.

The secondary objective is to determine the overall complete and partial responses after 6 months of therapy. The response rate will be reported as a proportion and 95% exact confidence interval.

Exploratory Objectives

Treatment failure (treatment failure defined as: administration of additional systemic therapy for chronic GVHD, malignancy relapse or mortality) by 6 months from study enrollment.

Time to treatment failure will be defined as study enrollment to failure event. Kaplan-Meier methods will be used to estimate the distribution for time to treatment failure. The failure rate at 6 months will be estimated from the Kaplan-Meier curve, and the rate and 95% confidence interval will be reported.

Time to non-relapse mortality will be computed as study enrollment to non-relapse death. Cumulative incidence methods will be used to estimate the distribution with relapses and relapse related deaths as competing events. The rate at 6 months will be estimated from the curve along with 95% confidence intervals.

For subjects treated on the extension study, the response rate at 12 months will be reported as a proportion and 95% exact confidence interval.

For subjects on steroids at baseline, we will explore the change in dose of steroids at 6 months. We will calculate the average percent change in dose for each subject along with a 95% CI. We will also determine the number and proportion of subjects that had a dose reduction greater than 50% as well as an exact 95% confidence interval.

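### The 16-responder success rule is given only for 42 subjects, although 47 are dosed and the full analysis set can be any size up to 47; stage 1 is worded as 18 treatment completers

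*Combined protocol and SAP*

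**What the plan says.** All of this is in Section 10.1 unless noted.

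- **Design.** Null response rate 25%, alternative 45%. Stop for futility at 4 or fewer of 18. At 42 subjects, 15 or fewer is failure, and "If 16 or more respond then further investigation is warranted". Stated power is 84% and stated significance level 0.044.
- **Number dosed.** "to account for dropout rate of approximately 10%, the study will dose 47 subjects". The protocol summary agrees: "A sample size of 47 subjects dosed (42 evaluable subjects and estimated 10% dropout".
- **Population.** "The full analysis set will include all subjects that are evaluable at 6 months as well as subjects who are considered a treatment failure", deaths included. "Subjects who drop out of the study prior to 6 months for reasons unrelated to treatment will be excluded from the full analysis set". Section 10.2.1 says of the primary analysis: "This analysis will be conducted on the full analysis set".
- **Stage 1.** "The first stage will occur once 18 subjects have completed 6 months of treatment".
- **Response.** The primary endpoint is complete or partial skin/joint response at 6 months, and it requires no added systemic chronic GVHD treatment, no relapse and no death. A wider definition serves the interim: "for the purpose of the stopping rules, responses will include complete and partial responses in skin and/or joint", with further clinician-rated and patient-reported improvements also counting.

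**The concern.** The go/no-go decision needs a numerator, a denominator and a cut-off that are fixed in advance. The cut-off is tied to 42. The denominator depends on how many of the 47 turn out evaluable, and no text says which 42 are tested or what happens at 40 or 45. A cut-off of 16 is a weaker hurdle in a larger set, so the stated error level can be exceeded. In an open-label trial the choice should not be left until responses are known.

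Stage 1 raises a related problem. If the 18 are only those who finished six months of drug, subjects who died, relapsed or needed new therapy before then are not among them. The interim set would then look better than the population on which the trial is finally judged.

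**Working it through.** **Inputs (Section 10.1).** n1 = 18, stop at 4 or fewer; success at 16 or more of 42; p0 = 0.25, p1 = 0.45; 47 dosed; dropout about 10%.

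**Formula.** For set size n and cut-off c, with X1 ~ Bin(18, p):

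P(success) = Σ over x = 5,…,18 of P(X1 = x) × P(Bin(n − 18, p) ≥ c − x).

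**The plan's own figures.**
- n = 42, c = 16: power at 0.45 is 0.841, which matches the stated 84%.
- Error rate at 0.25 is 0.0397, or P(Bin(42, 0.25) ≥ 16) = 0.0416 if the futility stop is ignored. The stated 0.044 is not reproduced exactly; the true value is lower, so this difference does no harm.
- 42 / 0.90 = 46.7, rounded up to 47, which matches.

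**Cut-off kept at 16 in a larger set.**

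| Set size | Error rate at 25% | Power at 45% |
|---|---|---|
| 42 | 0.040 | 0.841 |
| 43 | 0.048 | 0.865 |
| 44 | 0.058 | 0.885 |
| 45 | 0.069 | 0.902 |
| 46 | 0.081 | 0.915 |
| 47 | 0.094 | 0.925 |

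**How often the set exceeds 42.** Assume each dosed subject is excluded independently with probability d, so set size ~ Bin(47, 1 − d). Only 10% is the plan's figure; 5% and 15% are assumptions that show the range.

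| d | P(set > 42) | Error rate averaged over set size |
|---|---|---|
| 5% | 0.92 | 0.066 |
| 10% | 0.49 | 0.044 |
| 15% | 0.15 | 0.028 |

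At 10%, the error rate given a set above 42 is 0.059. The average returns to 0.044 because smaller sets are conservative: at 41 subjects power is 0.811 and at 40 it is 0.777.

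**Stage 1 as completers only.** The documents give no early-failure rate, so let a share f fail early without response. If the rate among all treated is 25%, the rate among completers is 0.25 / (1 − f), and P(stop) = P(Bin(18, 0.25 / (1 − f)) ≤ 4).

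| f (assumed) | Completer rate | P(futility stop) |
|---|---|---|
| 0 | 0.250 | 0.52 |
| 5% | 0.263 | 0.47 |
| 10% | 0.278 | 0.41 |
| 20% | 0.313 | 0.29 |

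The final error rate barely moves. Even if stage 1 never stopped the trial, it would rise only from 0.0397 to 0.0416, about 0.002.

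**Which non-completers are unscored.** New systemic therapy, relapse and death are non-response by the endpoint definition in Section 10.1, and Section 5.1.1 counts prednisone above the enrollment dose as new therapy. For a toxicity stop, Section 5.4 places the last GVHD evaluation at the end of 6 months, and Section 5.6 lets subjects who stop the drug stay in the study. That leaves subjects who go for toxicity or another treatment-related reason, have none of those events, and have no month-6 assessment. They are not excluded by Section 10.1, but no text gives them a response status. The table in Section 5.2 adds doubt: under a heading on stopping the drug, it speaks of removal from the study, whereas Section 5.6 treats study withdrawal as a separate step after which no further data may be collected.

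**The case against.** **The planned dropout rate makes the cut-off harmless on average.** At 10% the averaged error rate is 0.044 and averaged power is 0.839, and 0.094 needs all 47 in the set. This stands as a limit on size. It does not supply the missing rule: about half the time the set would exceed 42, and the level then depends on a choice made with the data in view.

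**The consequence is limited.** The primary report is a proportion with an exact 95% interval at whatever size is reached. With 16 responders the lower limit is 0.236 at 42 and 0.209 at 47, so readers would see that 25% is not excluded. This is fair, but the statement on further investigation still rests on the cut-off.

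**Stage 1 may be loosely worded rather than restrictive.** That is possible, and the effect on the error rate is negligible. The cost is weaker futility stopping, and only if the literal reading is applied.

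**Stronger readings.** A reader might infer that no text makes treatment-related non-completers non-responders. The documents do not support this, because the endpoint definition already settles new therapy, relapse and death, and most toxicity stoppers remain due for month-6 evaluation. A reader might also infer that such subjects could be dropped, inflating the response rate. Section 10.1 does not permit that, since only dropouts unrelated to treatment are excluded. Nor does an assessment at an early safety visit stand in for the endpoint, which is fixed at 6 months with a 14-day window.

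**Conclusion.** The point holds for the cut-off and for the stage 1 wording. The cut-off exceeds its stated level as soon as the set has 43 subjects (0.048) and reaches 0.094 at 47. Given a set above 42 at the planned 10% exclusion rate, the error rate is 0.059. These figures are exact for the rule as written; the probabilities of set size rest on independent exclusions, and the 5% and 15% rates are assumed. It would be wrong to say that the design runs at 0.094, or that it is inflated on average under its own dropout assumption.

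The stage 1 issue costs futility protection rather than error control, by an amount that depends on an early-failure rate the documents do not give. The unscored group is small and needs one sentence. Overall severity is minor to moderate: the gap concerns the decision rule, but it is easily closed.

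**What to change.** 1. **Cut-off.** Choose one of two rules before the data are reviewed.
   - Decide on the first 42 full-analysis-set subjects in order of enrollment. Error rate 0.040, power 0.84; up to 5 subjects then inform only the estimate. A cut-off is still needed if fewer than 42 qualify.
   - Print cut-offs by set size: 15 for 36–39, 16 for 40–42, 17 for 43–45, 18 for 46–47. The largest error rate is 0.0439 (15 of 39), even if stage 1 never stops the trial, so the table does not depend on the wider interim response definition. The cost is power at some sizes: 0.798 at 43, 0.815 at 46, 0.777 at 40, 0.710 at 36. Averaged at 10% exclusions, power is 0.817 against 0.839 with 16 kept throughout.
2. **Stage 1.** Define the 18 by the full-analysis-set rule, so that early treatment failures are among them as non-responders.
3. **Residual group.** State that a dosed subject with no month-6 assessment for a treatment-related reason counts as a non-responder. Reconcile the removal wording in Section 5.2 with Sections 5.4 and 5.6, so that it is clear who remains under evaluation.

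The changes are to wording only; the reported rate may be slightly lower. A sensitivity analysis of all dosed subjects, with missing as non-response, is optional.
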